Study Protocol

Official Title: Preoperative Levator Ani Muscle Injection and Pudendal Nerve Block With Bupivacaine and Dexamethasone for Improved Pain Control After Vaginal Reconstructive Surgery: A Three-Arm Randomized Controlled Trial

ClinicalTrials.gov ID (NCT number): NCT03040011

Protocol Date: 10/24/2019

Scientific Background

Many major gynecologic surgeries are increasingly becoming outpatient procedures (1-3). One criterion for same-day discharge is adequate pain control. Despite this, many women report suboptimal pain control after discharge following vaginal surgery (4). Furthermore, at 6 weeks postoperatively, only 50% of patients felt that they had fully recovered from surgery (4). Thus, even though a minimally invasive approach, there are areas for improvement in postoperative recovery after vaginal surgery.

Various local anesthetic techniques, including pudendal nerve blocks, have been studied as forms of preemptive analgesia to improve pain associated with vaginal surgery. While the methodologies vary making direct comparison difficult, the studies assessing preemptive analgesia at the time of vaginal surgery have yielded mixed results, particularly for apical support procedures (5-9) and an effective and generalizable way to reduce postoperative pain in a population of Female Pelvic Medicine and Reconstructive Surgery patients undergoing vaginal reconstructive surgery with apical suspension procedures has not been defined.

We utilize a novel injection technique in which we inject the study medication via a transobturator approach into the levator ani muscles directly. We utilized this approach in addition to the pudendal nerve blockade to deliver study medication to the levator ani muscles themselves and any distal nerve branches of the levator ani nerve, with the idea that this would decrease pain and edema at the operative site and improve postoperative pain control. We add dexamethasone to bupivacaine for the intervention group because of its known anti-inflammatory qualities (10). These anti-inflammatory properties have been translated to the surgical realm and the addition of perioperative perioperative recovery in multiple disciplines, including gynecology (11-15).

Study Objectives

Our primary aim is to determine if bilateral transobturator levator ani muscle injections and transvaginal pudendal nerve blocks with bupivacaine and dexamethasone improve postoperative pain measured by the numerical rating scale (NRS) on postoperative day 1 after vaginal reconstructive apical support procedures.

Our secondary aims include postoperative nausea and vomiting (measured by the postoperative nausea and vomiting score), analgesic consumption (measured in morphine equivalents), same-day discharge, postoperative pain at 6 hours, 48 hours, 72 hours and 1 week (measured by the NRS), need for either self-catheterization or indwelling catheter, safety and adverse events, and time to resume normal activity (measured by the activities assessment scale at 1,2,6 and 12 weeks postoperatively).

Study Design & Methods

We performed a 3-arm, double-blind, randomized, placebo-controlled trial of bilateral transobturator levator ani muscle injections and transvaginal pudendal nerve blocks

prior to native tissue vaginal apical support procedures for pelvic organ prolapse. Women were randomized to one of three study medication groups distributed over 4 injection sites: 22mL of 0.9% saline (placebo group), 22 mL of 0.25% bupivacaine (bupivacaine group), or 20 mL of 0.25% bupivacaine with 4mg (2mL) of dexamethasone (combined group).

Recruitment occurred and written informed consent was obtained during regularly scheduled preoperative office visits. If no preoperative visit was scheduled, informed consent was performed by telephone and the consent form was either mailed to the patient or signed on the morning of surgery. Block randomization occurred 1-2 days prior to scheduled surgery in a 1:1:1 ratio by a research coordinator not involved in study intervention or outcome assessment. The randomization scheme was stored in a password protected, secure location and only accessed by this research coordinator. We also took additional steps to ensure a double-blinded design. After randomization but before the start of the prolapse procedure, pharmacy personnel delivered the study medication to the operating room in a single, clear syringe labeled "Study Medication" and the corresponding study identification number. All syringes were identical. Additionally, normal saline, bupivacaine and dexamethasone are all clear solutions, which allowed us to blind physicians to the study medication being administered. Patients were also blinded to the study intervention until 12 weeks of follow-up.

All 3 study groups received transobturator levator ani muscle injections and pudendal nerve blocks with either saline, bupivacaine alone or bupivacaine and dexamethasone according to randomization. The study intervention was performed after the induction of general anesthesia and prior to the start of the prolapse repair. After the patient was placed in dorsal lithotomy position, sterile preparation occurred, and a urethral catheter was inserted. The bilateral transobturator levator muscle injections were performed first. The superior medial aspect of the obturator foramen was identified by palpation approximately 2-3 cm lateral and 2-3 cm inferior to the clitoris. With the thumb palpating the superior medial aspect of the obturator foramen, the index and middle finger were inserted into the vagina to confirm identification of the obturator foramen. A spinal needle was then inserted through the superior medial aspect of the obturator foramen through the obturator internus muscle. The trajectory of the needle at this point was angled slightly posteriorly towards the ischial spine, traveling parallel to the arcus tendineus levator ani and arcus tendineus fascia pelvis. The spinal needle was advanced to the level of the ischial spine, maintaining the same trajectory and with the vaginal hand ensuring that the spinal needle did not perforate the vaginal wall. Once the tip of the needle was at a depth where it had reached the ischial spine, aspiration was performed to ensure no intravascular needle placement and the study medication was injected. Bilateral pudendal nerve blocks were performed transvaginally after the transobturator injections. The pudendal nerve blocks were performed according to previously described technique (21,22). Five milliliters of study medication were injected at each of the four injection sites for a total of 20 mL of study medication. The intervention was performed by one of five attending surgeons or one of four urogynecology fellows. After the interventions, the vaginal reconstructive procedures were performed as usual by the attending surgeon and surgical team. Both fellows and

residents participated in these vaginal reconstructive surgeries, however for study purposes, resident physicians were not permitted to administer either the study injections.

To standardize care, all study participants received the same institutional induction and intraoperative enhanced recovery after surgery general anesthesia protocol, full details of which have been previously published (23). In summary, patients received intravenous propofol, ketamine, lidocaine, muscle relaxant and dexamethasone for induction and intravenous ketamine and lidocaine for maintenance (23). The intravenous dexamethasone given upon induction is part of the protocol to prevent postoperative nausea and vomiting. To standardize intraoperative local anesthetic, the amount of additional local infiltration was limited to 50ml of 0.5% lidocaine with epinephrine. According to our ERAS protocol, all surgeries were planned to be same-day surgeries. Any deviations from protocol were documented.

Our primary outcome was a numeric rating scale (NRS) pain score on postoperative day (POD) one. The NRS is an eleven-point scale ranging from 0 to 10 presented visually on a horizontal line. Higher scores represent more postoperative pain.

Secondary outcomes included pain scores at additional timepoints (6 hours after surgery, POD 2, POD 3 and 1 week after surgery), same day discharge rates, voiding status at time of discharge, postoperative narcotic consumption measured in oral morphine equivalents, postoperative ibuprofen consumption, postoperative nausea and vomiting (PONV), postoperative activities assessment, and adverse events. PONV was assessed using the PONV Intensity scale, a four-question assessment to measure clinically significant nausea and vomiting with higher scores signifying more clinically significant PONV (26). Time to resume normal activities was measured by the activities assessment scale (AAS), a 13-point scale on which patients rate their difficulty performing a range of activities from "No difficulty" to "Not able to do it." A final score ranging from 0-100 is transformed, with higher numbers reflecting less difficulty with activities (27). Assessments were completed by the patient at home and mailed to research staff upon completion. Women were followed for 12 weeks postoperatively and no additional office visits were required as part of the research protocol.

Eligibility Criteria

Women were eligible for inclusion if they were ≥18 years old and scheduled for a vaginal native tissue repair with apical support procedure (uterosacral ligament suspension, sacrospinous ligament fixation, levator myorrhaphy or colpocleisis) and able to undergo general anesthesia. Concomitant procedures including hysterectomy, anterior and posterior colporrhaphies, perineorrhaphies and midurethral sling placements were permitted. All patients needed to be available for at least 12 weeks of follow-up. Women were excluded for any of the following reasons: planned mesh-augmented apical support procedure or mesh excision, laparoscopic, robotic or abdominal surgery, known adverse reaction or allergy to intervention medication, evidence of fistula or infection, chronic pelvic pain as an active issue, daily opiate

consumption, history of pelvic radiation, daily steroid use, diabetes mellitus, immunosuppression, planned surgery under regional anesthesia, non-English speaking or inability to complete questionnaires, bleeding diatheses, or weight less than 50kg. We incorporated a weight less than 50kg as an exclusion criterion to ensure that the bupivacaine dosage was below the weight-based maximum dose, as recommended by our anesthesia colleagues (16).

Statistical Analysis Plan

All results will be analyzed by intention-to-treat based upon the study group to which subjects were randomized. One-way ANOVA, Kruskal Wallis, Chi-square, and Fisher's Exact will be used to compare continuous and categorical variables, respectively. Based upon prior studies demonstrating that pain after vaginal surgery ranges from a 2 to 5 on numeric scales (range 0-10) and literature suggesting that a 33% decrease in pain is clinically significant, we elected to assess a 2-point change in NRS scores between treatment groups (5,7,9,28). Based upon an ANOVA evaluated at the 2-sided 0.05 significance level and a standard deviation of 17.5, a sample size of 21 patients per arm provided 90% power to detect a 2-point change in NRS scores. To account for 20% attrition, we increased to 25 patients per arm for a total of 75 women.

We hypothesized that concurrent bilateral transobturator levator ani muscle injections and transvaginal pudendal nerve blocks with bupivacaine and dexamethasone performed prior to vaginal native tissue apical prolapse repair would result in statistically significant improved pain scores on postoperative day one.

References

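### Adverse events fall under the intention-to-treat rule by randomised group, with no safety set by drug received: a small effect and a cheap correction

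*Combined protocol and SAP*

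**What the plan says.** **Adverse events are an outcome.** Study Objectives lists "safety and adverse events" among the secondary aims. The secondary outcomes in Study Design & Methods end with "postoperative activities assessment, and adverse events".

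**Analysis set.** The Statistical Analysis Plan opens with "All results will be analyzed by intention-to-treat based upon the study group to which subjects were randomized". It defines no safety or as-treated set and makes no exception for harms.

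**Timing.** Study Design & Methods says "Block randomization occurred 1-2 days prior to scheduled surgery in a 1:1:1 ratio" and, later, "The study intervention was performed after the induction of general anesthesia and prior to the start of the prolapse repair". It also says "All 3 study groups received transobturator levator ani muscle injections and pudendal nerve blocks", which describes the groups and does not count the women injected.

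**Collection.** After describing the nausea and activity scales, the same section says "Assessments were completed by the patient at home and mailed to research staff upon completion". Follow-up is 12 weeks, and "no additional office visits were required as part of the research protocol". No section says how adverse events are defined, elicited or recorded.

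**The concern.** Analysis by randomised group protects the efficacy comparison. Harms are a different question: what happened to women exposed to each drug? A rule that covers every result mixes the two. Allocation comes a day or two before exposure, and in that interval an operation can be cancelled or a woman can withdraw. Where no preoperative visit was scheduled, the consent form could be signed as late as the morning of surgery, which is after allocation. Under the rule as written, a woman who drops out in that interval counts as exposed in the adverse-event table. If the wrong syringe were used, the event would be credited to the wrong drug.

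The protocol describes its injection technique as novel, and the arms have 25 women each. The harms table should therefore state clearly who was exposed, to what, and how many were followed for events.

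**Working it through.** The documents give no adverse-event rate, no number of uninjected women and no safety sample size, so there is no plan figure to reproduce. The check shows how far the two analysis sets can differ.

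**Inputs**
- Women randomised per arm: 25 (75 in total), from the Statistical Analysis Plan.
- Uninjected women per arm, u: not given. Assumed 0 to 2, with 5 as an extreme.
- Events per arm, x: not given. Assumed 3, all in injected women.

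**Formulas**
- Rate by randomised group = x / 25
- Rate among injected women = x / (25 - u)
- Relative dilution = 1 - (25 - u)/25 = u/25

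| u | By randomised group | Among injected | Relative dilution |
|---|---|---|---|
| 0 | 3/25 = 12.0% | 3/25 = 12.0% | 0% |
| 1 | 3/25 = 12.0% | 3/24 = 12.5% | 1/25 = 4% |
| 2 | 3/25 = 12.0% | 3/23 = 13.0% | 2/25 = 8% |
| 5 | 3/25 = 12.0% | 3/20 = 15.0% | 5/25 = 20% |

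The relative dilution depends only on u, not on x.

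**Direction**
- The table holds only if uninjected women have no events. If one uninjected woman had surgery and a surgical complication, the randomised-group rate would be (3 + 1)/25 = 16.0% against 3/24 = 12.5% among the injected, so the shift would be upwards.
- If a woman randomised to placebo received active drug and had an event, that event would add 1/25 = 4 percentage points to the placebo rate.
- If u is the same in every arm, the risk ratio is unchanged, because (x1/25)/(x2/25) = (x1/(25 - u))/(x2/(25 - u)) = x1/x2. The risk difference shrinks by the factor (25 - u)/25.

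**Source of adverse events.** No arithmetic applies here. The sentence on mailed assessments follows the descriptions of the two questionnaires and does not name adverse events. The same outcome list includes same-day discharge and voiding status at discharge, which arise before the woman goes home. The section also says that protocol deviations were documented. The absence of extra research visits leaves room for routine postoperative visits. The text names no adverse-event source, and it excludes none.

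**The case against.** The strongest reply is that nothing in the documents shows the problem occurring. The groups are described as injected according to allocation, and each syringe carried the study identification number. No uninjected or wrongly treated woman is reported. If there were none, the two analysis sets are identical. Even with one or two per arm, the same three events are simply divided by 24 or 23 instead of 25. Conversion during the repair is not an example, because the injection comes before the repair starts. All of this stands, and it limits the point to a gap in the rule with a small numerical effect. It does not remove the gap: the description is at group level, and the plan does not say how a woman without exposure would be handled in the harms analysis.

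Two stronger readings are tempting, and the documents support neither.

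- **Mailed forms as the only source.** A reader might infer that events in women who return nothing are lost. Applying the plan's 20% attrition would then leave 0.20 × 75 = 15 women without data and make a true 10% rate read as 0.10 × 0.80 = 8%. But the mailing sentence is not tied to adverse events. The 20% is an allowance in the sample size for the day-1 pain score. The plan also nowhere says that non-returners count as event-free.
- **Rates always pushed down.** A reader might infer that the rule always understates harm. As shown above, misallocation and surgical events in uninjected women can move a rate the other way, and nothing suggests that such losses would differ by arm.

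**Conclusion.** The point holds as a low-severity improvement. The intention-to-treat rule covers adverse events, no safety set is defined, and allocation precedes exposure by 1-2 days, so the rule would misplace any randomised woman who was not injected or who received another arm's drug. The size is 0% if there is no such woman and a 4-8% relative dilution if 1 or 2 of 25 per arm are uninjected and event-free. Those numbers are assumptions, because the documents report none. The missing adverse-event source is an omission of detail. It is worth filling, but it is not evidence that events went uncollected.

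**What to change.** 1. In the Statistical Analysis Plan, limit the intention-to-treat rule to the efficacy outcomes.
2. Define a safety set: all women who received any study injection, analysed by the drug actually received.
3. Report per arm the numbers randomised, injected and with adverse-event follow-up, and use the last as the denominator for event rates.
4. State the source and window for adverse events: existing operative, anaesthesia, recovery and routine-visit records through 12 weeks, whether or not mailed forms are returned.

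The cost is a few sentences in the plan and record abstraction for at most 75 women, with no new visits. The one small downside is that safety and efficacy tables may have different denominators, which a table footnote can explain.

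### The printed standard deviation of 17.5 cannot belong to a 0-10 pain score and does not give the stated 90% power; and if the cited scores of 2 to 5 are control scores, that 90% does not cover a 33% decrease

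*Combined protocol and SAP*

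**What the plan says.** Study Design & Methods fixes the endpoint: "Our primary outcome was a numeric rating scale (NRS) pain score on postoperative day (POD) one". It also fixes the scale: "The NRS is an eleven-point scale ranging from 0 to 10".

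The Statistical Analysis Plan gives two premises for the target. One is that "pain after vaginal surgery ranges from a 2 to 5 on numeric scales (range 0-10"; the other is a relative threshold, followed by the choice of target: "literature suggesting that a 33% decrease in pain is clinically significant, we elected to assess a 2-point change in NRS scores between treatment groups". For an ANOVA at the two-sided 0.05 level, it then cites "a standard deviation of 17.5, a sample size of 21 patients per arm provided 90% power to detect a 2-point change in NRS scores". Enrolment is set at 25 per arm, 75 in all, to allow for attrition. No unit is given for the SD and no pattern of means for the three arms. The plan does not say whether scores of 2 to 5 were seen in untreated patients, treated patients or both.

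The analysis methods are overall tests: "One-way ANOVA, Kruskal Wallis, Chi-square, and Fisher's Exact will be used to compare continuous and categorical variables". The aim in Study Objectives and the closing hypothesis are about the combined bupivacaine-dexamethasone treatment, which the hypothesis says "would result in statistically significant improved pain scores on postoperative day one".

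**The concern.** The SD and the 2-point target are the two inputs behind 21 per arm. An SD of 17.5 is wider than the whole scale, so the power statement cannot be checked as printed.

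The target raises a separate question that correcting the SD does not settle. Read plainly, the two premises lead to a difference smaller than 2 points. A reader could then take the 90% to cover the decrease that the plan cites as clinically significant, when it applies to a larger one. This matters most for a result that falls short of significance. The plan names no combined-versus-placebo estimate, so the overall test alone would not show which differences between those two arms remain compatible with the data.

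**Working it through.** **Inputs from the documents.** Three arms at 1:1:1; 21 per arm; ANOVA, alpha 0.05; difference 2 points; SD 17.5; scale 0 to 10; cited scores 2 to 5; relative decrease 33%; 25 per arm enrolled.

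**Inputs assumed.** The pattern of arm means, and an SD of 1.75 where stated. Neither is in the documents.

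**Formula.** Power is the upper tail of a noncentral F distribution with 2 and 3(n − 1) degrees of freedom and noncentrality λ = n × S / SD², where S is the sum of squared deviations of the arm means from their average. For n = 21 the critical value is F(2, 60) = 3.15. Equally spaced means (0, 1, 2) give S = 2. One arm different (0, 0, 2) gives S = 8/3.

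**1. Is an SD of 17.5 possible?** The largest sample SD for 21 values on 0 to 10 comes from ten scores of 0 and eleven of 10: √[(100 × 10 × 11 / 21) / 20] = 5.12. So 17.5 is impossible on this scale.

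**2. The plan's own power figure (n = 21, 2 points).**

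| SD | Means | λ | Power | n per arm for 90% |
|---|---|---|---|---|
| 17.5 (printed) | 0, 1, 2 | 21 × 2 / 306.25 = 0.137 | 6.0% | 1,939 |
| 17.5 (printed) | 0, 0, 2 | 21 × 2.667 / 306.25 = 0.183 | 6.3% | 1,455 |
| 1.75 (assumed) | 0, 1, 2 | 21 × 2 / 3.0625 = 13.71 | 90.9% | 21 |
| 1.75 (assumed) | 0, 0, 2 | 21 × 2.667 / 3.0625 = 18.29 | 97.0% | 16 |

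Other readings of the printed SD do not rescue it. Means of 0, 2, 4 give 9.1%. A two-sample t-test gives 6.5% two-sided or 10.0% one-sided. An SD of 1.75 with equally spaced means returns exactly 21 per arm. It is also the same standardized effect as 20 points with an SD of 17.5 on a 0-100 scale. A decimal slip and a scale slip therefore both fit.

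**3. The target against its premises, if 2 to 5 are control scores.**
- 0.33 × 2 = 0.66; 0.33 × 3.5 (the midpoint) = 1.155; 0.33 × 5 = 1.65.
- Two points is 2/5 = 40% of the highest cited score and 2/2 = 100% of the lowest. It equals 33% only at 2/0.33 = 6.1.

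**4. Power at those smaller differences, taking 90% at 2 points as true.** This needs no SD. Power of 0.90 with 2 and 60 degrees of freedom requires λ = 13.31, and λ scales with (d/2)². For 25 evaluable per arm, λ is multiplied by 25/21, with 2 and 72 degrees of freedom.

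| d | λ, n = 21 | Power, n = 21 | Power, n = 25 |
|---|---|---|---|
| 1.65 | 9.06 | 75% | 83% |
| 1.155 | 4.44 | 44% | 51% |
| 0.66 | 1.45 | 17% | 19% |

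The SD implied by λ = 13.31 is √(42/13.31) = 1.78 with equally spaced means, or √(56/13.31) = 2.05 with one arm different. Under the assumed SD of 1.75, power at 1.65 points is 77% or 88% with 21 per arm, and 84% or 93% with 25, for the same two patterns.

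**5. What a combined-versus-placebo interval would show.** The half-width of the 95% interval is t(60) × SD × √(2/21) = 2.00 × SD × 0.309. That is 1.08 points at SD 1.75 and 1.27 at SD 2.05. If the true difference were zero, the interval would exclude a 1.65-point reduction about 85% or 73% of the time, and a 0.66-point reduction about 22% or 18%.

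**The case against.** The strongest reply has four parts.

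**The SD is a misprint, so 6% and 1,939 per arm measure nothing about the design.** This largely stands. A reader might infer from the printed SD that the trial is hopelessly underpowered. The documents do not support that: 17.5 is impossible on the stated scale, and a shift of one decimal place reproduces 21 per arm. The 6% shows that a printed input is wrong; it does not estimate the trial's power.

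**The target need not conflict with its premises.** A reader might infer that 2 points certainly contradicts the 33% threshold. That goes too far. The range of 0.66 to 1.65 holds only if 2 to 5 are control scores, which the plan does not say. If they were scores after a 33% decrease, the untreated scores would be about 2/0.67 = 3.0 to 5/0.67 = 7.5 and the decrease about 1.0 to 2.5 points, which contains 2. The plan also says only that 2 points was elected, not that it equals 33% of anything. A trial may aim above a minimum important change, and the cited sources, which cannot be seen here, may give a reason. The target point is therefore conditional.

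**The gap is small where it matters most.** At the top of the range this stands: 83% power at 1.65 points with 25 evaluable per arm, and more if only one arm differs. The 17% at 0.66 is the worst case. Lower in the range the gap is large.

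**The plan nowhere says that a non-significant test would exclude a 33% decrease.** Correct; that error should not be attributed to it. The interval is worth adding for a different reason: the hypothesis concerns the combined arm, while only overall tests are named.

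**Conclusion.** The power statement is wrong as written. This part is certain: an SD of 17.5 cannot occur on a 0-10 score and gives about 6% power at 2 points, not 90%. The likely cause is a decimal or scale slip. Under an assumed SD of 1.75, power is 91% with equally spaced means or 97% with one arm different, so nothing here shows that 21 per arm is too few for a 2-point difference.

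The second part is conditional on 2 to 5 being control scores. In that case the 90% applies to a larger effect than the 33% decrease cited as clinically significant. The shortfall is modest at the top of the range and large below it. The power figures for the smaller differences also take the plan's 90% at 2 points as true. If the range includes treated patients, the mismatch may shrink or disappear.

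**What to change.** Leave the sample size unchanged and make three changes.

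1. Correct the SD of 17.5, state the assumed means of the three arms, and restate the power from those planning values rather than from observed data.
2. Say whether 2 to 5 are control scores. If they are, state that 2 points exceeds a 33% decrease, say why it was chosen, and give the power at 1.65 points and below.
3. Report the combined-versus-placebo difference in postoperative day 1 NRS with its 95% confidence interval beside the overall test, dated as an addition to the 10/24/2019 plan.

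The cost is a less favourable stated power for effects below 2 points, and one added contrast. No more patients are needed. With a half-width of about 1.1 to 1.3 points at 21 per arm (assumed SD 1.75 to 2.05), the interval informs only the upper part of the 0.66 to 1.65 range.

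### The sample size rests on an SD of 17.5 for a 0-10 pain score, which is impossible on that scale, so 90% power at 21 per arm cannot be reproduced

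*Combined protocol and SAP*

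**What the plan says.** Under Study Design & Methods, the primary outcome is the pain score on postoperative day 1: "The NRS is an eleven-point scale ranging from 0 to 10 presented visually on a horizontal line". The Statistical Analysis Plan keeps to this scale. It cites earlier pain levels of 2 to 5 on a 0-10 range and then sets the target: "we elected to assess a 2-point change in NRS scores between treatment groups". The sample size follows at once. It is based on an ANOVA at the two-sided 0.05 level, and the plan states: "a standard deviation of 17.5, a sample size of 21 patients per arm provided 90% power to detect a 2-point change in NRS scores". The number is then raised to 25 per arm, 75 in total, for 20% attrition.

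No section gives another SD, a unit or conversion for 17.5, a source for it, or the three arm means behind the calculation. The only 0-100 score in the documents is the activities assessment scale, which is a secondary outcome.

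**The concern.** The effect is 2 points on a scale only 10 points wide, yet the SD in the same sentence is 17.5, larger than the whole scale. The two figures cannot be on the same scale, and the text does not say that they are on different ones.

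This is the only variability figure behind the sample size and the 90% power statement. If it is wrong, a reader can check neither. That matters most if the trial finds no difference: whether such a result is informative depends on the SD that the design assumed and on how close it was to the SD observed.

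**Working it through.** **Inputs from the documents.** Three arms, 1:1:1; 21 per arm; ANOVA at 0.05; a 2-point difference; SD 17.5; stated power 90%. The arm means are not given. I take their range as 2 points and use the two extreme patterns: 0, 1, 2 (lowest power) and 0, 0, 2 (highest).

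**Is an SD of 17.5 possible?** The SD of any variable bounded by 0 and 10 is at most (10 − 0)/2 = 5. The largest sample SD in 21 patients occurs with ten scores of 0 and eleven of 10. The sum of squares is then (10 × 11/21) × 100 = 523.8, and √(523.8/20) = 5.12. So 17.5 cannot occur.

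**Does the stated power follow?** Power comes from the noncentral F distribution with 2 and 3 × (21 − 1) = 60 degrees of freedom and λ = n × Σ(mᵢ − m̄)²/SD².

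- Means 0, 1, 2: Σ = 2; λ = 21 × 2/17.5² = 0.137; power 6.0%.
- Means 0, 0, 2: Σ = 2.667; λ = 21 × 2.667/17.5² = 0.183; power 6.3%.

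For 90% power these inputs would need 1,939 or 1,455 patients per arm.

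**Other readings that keep 17.5 on the 0-10 scale.**

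- Steps of 2 points between successive arms (means 0, 2, 4): 9.1%.
- A two-sided comparison of two arms: 5.6% (normal) or 6.5% (t).
- A one-sided comparison of two arms (normal): 10.1%.
- 17.5 read as a variance (SD 4.18), with a 2-point range of means: 25% to 33%.

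None comes near 90%.

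**What could have produced 21?** At least two sets of inputs fit.

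- SD 1.75, means 0, 1, 2: λ = 21 × 2/1.75² = 13.71; power 90.9%. With 20 per arm it is 89.3%, so 21 is the first size to reach 90%. An SD of 17.5 with a 20-point difference on a 0-100 scale is the same calculation.
- SD 2.0, means 0, 0, 2: λ = 21 × 2.667/2.0² = 14.0; power 91.5%. With 20 per arm it is 89.97%, so 21 is again the first.

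**Sensitivity to the SD.** These SDs are assumptions and do not come from the documents. Each range runs from means 0, 1, 2 to means 0, 0, 2.

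| Assumed SD | Power, 21 per arm | Power, 25 per arm (all evaluable) |
|---|---|---|
| 1.75 | 91% to 97% | 95% to 99% |
| 2.0 | 81% to 91% | 88% to 96% |
| 2.5 | 61% to 75% | 70% to 82% |
| 3.0 | 46% to 58% | 53% to 66% |

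The largest SD that keeps 90% is 1.78 to 2.05 at 21 per arm and 1.95 to 2.25 at 25 per arm, depending on the pattern of means.

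**The case against.** The strongest reply is that this is a slip in reporting and not a failed calculation. Moving the decimal point gives 1.75, and under the least favourable 2-point pattern that SD returns exactly 21 per arm. It also explains the printed digits, which an SD of 2.0 does not. This makes 1.75 the more likely candidate, and it is a good reason not to call the trial underpowered. It does not settle the matter, because 1.75 appears nowhere in the documents and the means are not stated. Only the sponsor's calculation record can show what was used.

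Three narrower points have some force.

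- The limit of 2.05 holds only if the arm means span 2 points. If successive arms differed by 2 points each (0, 2, 4), 90% would hold at 21 per arm up to an SD of 3.55. A 4-point spread is a less natural reading when expected pain is 2 to 5, but the condition must be stated.
- With 20% attrition, 25 per arm leaves 25 × 0.8 = 20 patients. At SD 1.75 that gives 89.3% to 96.2%, so the low end falls short of 90% by less than one percentage point.
- If a calculation record exists, the correct SD with its source and the arm means repair the sentence by themselves. The sensitivity line is then an aid to the reader; without a record it becomes necessary.

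**Conclusion.** The error holds. An SD of 17.5 is impossible on the scale that the plan defines, and the printed inputs give about 6% power where 90% is stated. The 6% measures how far the sentence is from being reproducible; it says nothing about the power the trial actually has.

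Whether 90% was ever justified depends on an SD that the documents do not give. For a 2-point range of means and 21 per arm, it is justified under every pattern if the SD was at most 1.78 and under none if it exceeded 2.05. In between it depends on the unstated means. If the SD was 1.75, the missing means do not threaten the figure at 21 per arm.

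The correction is required, because the figure is the sole variability input to the primary sample size. Confidence is high: the bound on the SD needs no assumption, and the power result differs little between the two extreme patterns of means.

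**What to change.** Replace 17.5 with the SD actually used, on the 0-10 scale, taken from the sponsor's calculation record, with its unit and source. State the three assumed arm means and restate the power from them. For example:

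> Assuming a within-arm SD of [value] points on the 0-10 NRS [source] and arm means of [a, b, c], a one-way ANOVA at alpha 0.05 with 21 per arm gives [x]% power.

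Add one line giving the power at 21 per arm for SDs of 1.75, 2.0, 2.5 and 3.0 under both patterns of means. If no calculation record survives, say so and report that line in place of the single 90% figure. Do not insert 1.75 merely because it fits.

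The cost is one corrected sentence and one added line. The sample size, the test and the analysis do not change, and no further patients are needed. The drawback is that the restated power may look less favourable: with arm means spanning 2 points, 90% at 21 per arm could not be kept if the SD used was above 2.05.
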